10. SAFETY REPORTING

10.1. Definitions

Adverse Event (AE)	Any untoward medical occurrence in a participant to whom a medicinal product has been administered, including occurrences which are not necessarily caused by or related to that product.
Adverse Reaction (AR)	
An untoward and unintended response in a participant to an investigational medicinal product which is related to any dose administered to that participant.
 
The phrase "response to an investigational medicinal product" means that a causal relationship between a trial medication and an AE is at least a reasonable possibility, i.e. the relationship cannot be ruled out.
 
All cases judged by either the reporting medically qualified professional or the Sponsor as having a reasonable suspected causal relationship to the trial medication qualify as adverse reactions.

Serious Adverse Event (SAE)	
A serious adverse event is any untoward medical occurrence that:
 
 • results in death • is life-threatening • requires inpatient hospitalisation or prolongation of existing hospitalisation • results in persistent or significant disability/incapacity • consists of a congenital anomaly or birth defect. 
Other 'important medical events' may also be considered serious if they jeopardise the participant or require an intervention to prevent one of the above consequences.
 
NOTE: The term "life-threatening" in the definition of "serious" refers to an event in which the participant was at risk of death at the time of the event; it does not refer to an event which hypothetically might have caused death if it were more severe.

Serious Adverse Reaction (SAR)	An adverse event that is both serious and, in the opinion of the reporting Investigator, believed with reasonable probability to be due to one of the trial treatments, based on the information provided.
Suspected Unexpected	A serious adverse reaction, the nature and severity of which is not

Serious Adverse Reaction (SUSAR)	consistent with the information about the medicinal product in question set out: 
 • in the case of a product with a marketing authorisation, in the summary of product characteristics (SmPC) for that product • in the case of any other investigational medicinal product, in the investigator’s brochure (IB) relating to the trial in question.
----------------------------------	---

NB: to avoid confusion or misunderstanding of the difference between the terms “serious” and “severe”, the following note of clarification is provided: “Severe” is often used to describe intensity of a specific event, which may be of relatively minor medical significance. “Seriousness” is the regulatory definition supplied above.

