10.3. Causality

The relationship of each adverse event to the trial medication must be determined by a medically qualified individual according to the following definitions:

Relationship to Drug	Comment
Definitely	Previously known toxicity of agent; or an event that follows a reasonable temporal sequence from administration of the drug; that follows a known or expected response pattern to the suspected drug; that is confirmed by stopping or reducing the dosage of the drug; and that is not explained by any other reasonable hypothesis.
Probably	An event that follows a reasonable temporal sequence from administration of the drug; that follows a known or expected response pattern to the suspected drug; that is confirmed by stopping or reducing the dosage of the drug; and that is unlikely to be explained by the known characteristics of the subject's clinical state or by other interventions.
Possibly	An event that follows a reasonable temporal sequence from administration of the drug; that follows a known or expected response pattern to that suspected drug; but that could readily have been produced by a number of other factors.
Unrelated	An event that can be determined with certainty to have no relationship to the study drug.

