Moderate (2)	Mild to moderate limitation in activity, no or minimal medical intervention/therapy required.
Severe (3)	Marked limitation in activity, medical intervention/therapy required, hospitalizations possible.
Life-threatening (4)	The subject is at risk of death due to the adverse experience as it occurred. This does not refer to an experience that hypothetically might have caused death if it were more severe.
Death (5)	Death related to AE

AEs considered related to fluciclovine (¹⁸F) injection as judged by a medically qualified investigator or the Sponsor will be followed either until resolution, or the event is considered stable.

It will be left to the investigator's clinical judgment whether or not an AE/ AR is of sufficient severity to require the patient's removal from PET/CT scanning. A participant may also voluntarily withdraw from study procedures if they tolerate it poorly. Further details of withdrawal are presented in Section 7.7.

In the event of symptoms arising, participants will be given appropriate care and medical supervision until symptoms resolve, or the condition becomes stable. Every effort will be made to gather outcome data on patients through study follow-up, or general practitioner/ hospital staff unless the participant has specifically withdrawn consent to such efforts.

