10.6. SUSAR Reporting

Blue Earth Diagnostics will be responsible for reporting of all SUSARs to the relevant Competent Authority (MHRA in the UK) and to the REC and other parties as applicable. For fatal and life-threatening SUSARS, this will be done no later than 7 calendar days after the Sponsor or delegate is first aware of the reaction. Any additional relevant information will be reported within 8 calendar days of the initial report. All other SUSARs will be reported within 15 calendar days.

Principal Investigators will be informed of all SUSARs for the relevant IMP for all studies with the same Sponsor, whether or not the event occurred in the current study.

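### Protocol 10.1 tests causality more narrowly for a serious adverse reaction than for an adverse reaction, so on the natural reading a serious unexpected event suspected only by the sponsor does not trigger SUSAR reporting

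*Protocol*

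**What the plan says.** The definitions table in protocol section 10.1 builds up to the SUSAR in steps.

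- **Adverse reaction (AR).** The threshold is that "a causal relationship between a trial medication and an AE is at least a reasonable possibility, i.e. the relationship cannot be ruled out". On whose judgement counts, the row says: "All cases judged by either the reporting medically qualified professional or the Sponsor as having a reasonable suspected causal relationship" qualifies.
- **Serious adverse reaction (SAR).** This is an adverse event that is serious and is also, "in the opinion of the reporting Investigator, believed with reasonable probability to be due to one of the trial treatments".
- **SUSAR.** The row opens "A serious adverse reaction, the nature and severity of which is not" and continues with consistency against the product information. It has no wording of its own on causality or on who assesses it.

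Section 10.6 attaches the expedited duties to SUSARs. The sponsor "will be responsible for reporting of all SUSARs to the relevant Competent Authority" and to the ethics committee. On timing, "For fatal and life-threatening SUSARS, this will be done no later than 7 calendar days" after first awareness, with 15 calendar days for the others. The same section has principal investigators informed of all SUSARs.

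**The concern.** One would expect a serious adverse reaction to be an adverse reaction that is also serious. The SAR row does not say that. It starts again from an adverse event and sets its own causality test, which differs from the AR test in two ways: the sponsor's judgement is left out, and the wording moves from possibility to probability. When an event becomes serious, the relatedness test therefore becomes narrower.

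The SUSAR row takes its causality content from the term serious adverse reaction, so the narrower test carries through to expedited reporting. At stake is whether the text itself triggers a report to the authority and ethics committee, and a notice to investigators, when the sponsor suspects the product and the site does not.

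**Working it through.** The documents give no figure on this point and no arithmetic applies. The check is to set the definitions side by side, run test cases through them, and look for text elsewhere that repairs the gap.

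**1. The rows compared (protocol 10.1)**

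| Term | Starts from | Who judges | Causality threshold |
|---|---|---|---|
| AR | response to the product | reporter or sponsor | at least a reasonable possibility |
| SAR | adverse event that is serious | reporting investigator only | reasonable probability |
| SUSAR | serious adverse reaction | not stated | not stated |

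**2. Test cases: serious, unexpected events, with SUSAR read as a subset of the SAR row**

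| Case | SAE | AR | SAR | SUSAR |
|---|---|---|---|---|
| Investigator believes it related with reasonable probability | yes | yes | yes | yes |
| Investigator sees no relation, sponsor suspects one | yes | yes | no | no |
| Investigator thinks it only possibly related | yes | yes | not settled | not settled |
| Neither suspects a relation | yes | no | no | no |

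The second case is the clear gap. The sponsor's judgement is enough for an AR, but the SAR row does not admit it.

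The third case is less certain. A merely possible relation fits the AR wording, because it cannot be ruled out, but it need not amount to reasonable probability. The documents do not map reasonable probability onto the grades in section 10.3, so such an event is at risk of exclusion and not excluded outright. SAP 6.1 counts possibly, probably and definitely as related, so the study tables could show a related serious event that the protocol does not call a SAR.

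**3. Search for a repair elsewhere in the protocol**

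- Section 10.3: "The relationship of each adverse event to the trial medication must be determined by a medically qualified individual". The sponsor is not mentioned.
- Section 10.4: events considered related "as judged by a medically qualified investigator or the Sponsor will be followed either until resolution, or the event is considered stable". This admits the sponsor's judgement, but only for follow-up. The items to be recorded under 10.4 include the investigator's assessment of relatedness and no sponsor assessment.
- Section 10.5: all SAEs must be reported within 24 hours of the site's awareness, whatever the causality. The sponsor gets the information, but the classification does not change.
- Section 10.6: the sponsor must report SUSARs, and the definition is not widened.
- Section 10.7: the sponsor reviews all SAEs each quarter and cumulatively and may take action, but there is no rule for raising an event's causality or reclassifying it.

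None of these closes the gap. The AR row and the 10.4 follow-up rule take the wider view of who may judge, and the AR row and SAP 6.1 take the wider view of threshold. The SAR row is the outlier.

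**The case against.** **A softer reading of the SUSAR row.** The phrase serious adverse reaction can be taken as any AR, including one judged by the sponsor, that happens to be serious. That reading is possible and would remove the gap. It is not the natural one, because the same phrase is a defined term in the row directly above. If the sponsor means it, the correction below only makes it explicit.

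**Lost reports.** A reader might infer that sponsor-suspected events were missed, or that every such event is misclassified. The documents do not support this. The sponsor receives every SAE with no causality filter, reviews them all, and files the SUSAR reports itself. In the clear case the party with the suspicion is the party that reports, so no information is lost and it may well report anyway. The protocol also binds the trial to the UK regulations and GCP. Their text is not in the documents, so what they would require of these events is left out of this point.

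**The threshold limb.** Reasonable probability should not be equated with the grade Probably in 10.3, and the AR row's own wording is loose. This objection stands, and is why the limb is stated only as a risk.

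**Timing and volume.** The product is a single injection, the reactions described in section 9.1 are mild, adverse events are recorded up to one month after the scan (10.4), and section 11.3 states that recruitment was terminated early. This also stands and limits the practical effect. It does not remove it: section 10.5 sets no end date for SAEs, and section 10.2 makes Grade 3 and 4 laboratory abnormalities SAEs, with exceptions, so causality calls on SAEs already received are plausible.

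**Conclusion.** The point holds as an internal inconsistency in section 10.1 that is wrong as written, and it is minor. The AR and SAR rows disagree on who judges causality and on the threshold, and the SUSAR row inherits the disagreement. On the natural reading, a serious unexpected event suspected only by the sponsor lies outside the SUSAR trigger and hence outside the duties in 10.6. For an event judged only possibly related, exclusion is a risk and not a certainty.

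The conclusion assumes that the SUSAR row uses serious adverse reaction in the sense of the row above it. It concerns the definitions and does not show that any report was missed. The documents give no count of affected events, and few are expected. The primary endpoint, the sample size and the planned analyses are unaffected.

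**What to change.** In protocol 10.1, redefine a serious adverse reaction as an adverse reaction, as already defined in that section (judged by the reporter or the sponsor, at least a reasonable possibility), that meets any of the seriousness criteria. Leave the SUSAR row unchanged so that it inherits the corrected scope. Because recruitment has ended, also apply the corrected definition to the SAEs already received and document the result.

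The definition itself takes one sentence. To make it work, the sponsor's causality judgement must be recorded alongside the investigator's, which section 10.4 does not now provide for. The other cost is possibly a few more expedited reports. No new patient data are needed.

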10.2. Clinical laboratory abnormalities and other abnormal assessments as AEs and SAEs

Abnormal laboratory findings or other abnormal assessments (e.g. injection site) that are judged by the investigator as clinically significant will be recorded as AEs or SAEs if they meet the definitions given above. By definition, all CTCAE v4.0 Grade 3 and or 4 laboratory abnormalities should be reported as SAEs (unless specified otherwise below).

Clinically significant abnormal laboratory findings or other abnormal assessments that are detected during the study or are present at baseline and significantly worsen following the start of the study will be reported as AEs or SAEs. However, clinically significant abnormal laboratory findings or other abnormal assessments that are associated with the disease being studied, unless judged by the investigator as more severe than expected for the patient’s condition, or that are present or detected at the start of the study and do not worsen, will not be reported as AEs or SAEs. The investigator will exercise his or her medical and scientific judgment in deciding whether an abnormal laboratory finding or other abnormal assessment is clinically significant.

Incidental synchronous cancers findings noted on fluciclovine (¹⁸F) PET/CT images will be reported as medical events, and qualify for reporting as AEs due to their temporal relationship to fluciclovine (¹⁸F) administration.

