10.4. Procedures for Recording Adverse Events

All AEs observed by the investigator or reported by the patient up to 1 month after fluciclovine (¹⁸F) PET/CT are reported on the case report forms. A member of the research team will contact the participant by telephone 24 -72 hours and 1 month after completion of fluciclovine (¹⁸F) PET/CT to record any AEs that may have occurred after leaving the hospital. Patients will also attend a clinic visit 14 days post scan. All AEs reported by the patient will be clearly documented on the patient CRFs. The following information will be recorded: description, date of onset and end date, severity, investigator assessment of relatedness to fluciclovine (¹⁸F) injection, other suspect drug or device and action taken. Follow-up information should be provided as necessary.

AE severity

The National Cancer Institute's Common Terminology Criteria for Adverse Events (CTCAE) Version 4.03 (June 14, 2010) will be used to assess and grade event severity, including laboratory abnormalities judged to be clinically significant. The severity grading is provided below (Table 1).

Table 1. CTCAE (V4.03) AE Severity Grading

Severity (Toxicity Grade)	Description
Grade 1	Mild; asymptomatic or mild symptoms; clinical or diagnostic observations only; intervention not indicated.
Grade 2	Moderate; minimal, local or non-invasive intervention indicated; limiting age-appropriate instrumental ADL.*
Grade 3	Severe or medically significant but not immediately life-threatening; hospitalisation or prolongation of hospitalization indicated; disabling; limiting self care ADL**.
Grade 4	Life-threatening consequences; urgent intervention indicated.
Grade 5	Death related to AE

*Instrumental ADL refer to preparing meals, shopping for groceries or clothes, using the telephone, managing money, etc.

** Self care ADL refer to bathing, dressing and undressing, feeding self, using the toilet, taking medications, and not bedridden.

If the experience is not covered in the modified criteria, the guidelines shown in Table 2 below will be used to grade severity. It should be pointed out that the term “severe” is a measure of intensity and that a severe event is not necessarily serious.

Table 2. AE Severity Grading

Severity (Toxicity Grade)	Description
Mild (1)	Transient or mild discomfort; no limitation in activity; no medical intervention or therapy required. The subject may be aware of the sign or symptom but tolerates it reasonably well.

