6.1 Adverse Events

Adverse events (AE) will be coded using the Medical Dictionary for Regulatory Activities (MedDRA) version 17.1.

A treatment-emergent adverse event (TEAE) is defined as an AE with start date/time on or after the start/time of fluciclovine (¹⁸F) administration, or AEs with worsening intensity on or after the start date/time of fluciclovine (¹⁸F) administration.

AEs with unknown start date/time will be assumed to be treatment-emergent unless the end date/time is known to be before the fluciclovine (¹⁸F) administration.

Summary tables will be produced for all TEAEs occurring up to 42 days (i.e. occurring between day 1 and day 43) after the fluciclovine (¹⁸F) administration.

An overall summary of TEAEs will be created including:

- number of TEAEs and number of subjects with TEAEs,
- number of TEAEs and number of subjects with TEAEs associated with the injection site,
- number of serious TEAEs and number of subjects with serious TEAEs,
- number of subjects with TEAEs by CTCAE grade (Grade 1 to Grade 5),
- number of subjects with TEAEs by relationship to fluciclovine (unrelated, possibly related, probably related, definitely related and related, where related adverse events are those classified as possibly, probably and definitely related to fluciclovine ¹⁸F)

The number and percentage of subjects experiencing TEAEs will be presented by system organ class (SOC) and preferred term (PT). System organ class and preferred term will be presented in decreasing frequency of the total number of subjects with TEAEs. If a subject experienced more than one treatment-emergent adverse event, the subject will be counted once for each system organ class and once for each preferred term.

The number and percentage of subjects experiencing TEAEs will be presented by SOC, PT and CTCAE grade. SOC and PT will be presented in decreasing frequency of the total number of subjects with TEAEs. If a subject experienced more than one TEAE, the subject will be counted once for each SOC and once for each PT at the worst severity.

The number and percentage of subjects experiencing TEAEs will be presented by SOC, PT and relationship to study drug. SOC and PT will be presented in decreasing frequency of the total number of subjects with TEAEs. If a subject experienced more than one TEAE, the subject will be counted once for each SOC and once for each PT at the closest relationship to study drug.

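### Protocol 10.2 makes Grade 3/4 laboratory abnormalities SAEs by grade alone, with two exemptions, in conflict with the outcome-based definition in 10.1; SAP 6.1 does not separate such events in its serious-TEAE count

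*Protocol*

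**What the plan says.** Protocol 10.1 lists the outcomes that make an event serious: death, threat to life, hospital admission, lasting disability and birth defect. The admission criterion reads "requires inpatient hospitalisation or prolongation of existing hospitalisation". Other important medical events may be added case by case if they endanger the participant or need intervention to avert a listed outcome. No laboratory value or CTCAE grade appears in the list. A note closing the section says that seriousness means this definition and severity means intensity. Protocol 10.4 repeats that "a severe event is not necessarily serious".

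Protocol 10.2 opens in line with this: abnormal findings that the investigator judges clinically significant "will be recorded as AEs or SAEs if they meet the definitions given above". Its next sentence, presented as following by definition, says that "all CTCAE v4.0 Grade 3 and or 4 laboratory abnormalities should be reported as SAEs", with a bracketed qualifier pointing to exceptions further down. The paragraph after it supplies the exceptions. One covers findings "that are associated with the disease being studied, unless judged by the investigator as more severe than expected" for the patient's condition. The other covers findings "that are present or detected at the start of the study and do not worsen, will not be reported as AEs or SAEs". The same paragraph leaves clinical significance to the investigator.

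SAP 6.1 plans one summary line, "number of serious TEAEs and number of subjects with serious TEAEs", and a separate line by CTCAE grade. All SAEs are listed. The SAP does not say what makes an event serious.

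**The concern.** Two tests of seriousness stand side by side in the protocol. One asks what happened to the participant; the other asks how far a laboratory value lies from normal. The SAP takes whatever sites reported as serious and puts it into one count. If the grade rule is followed, that count can include events that 10.1 would not call serious, and nothing planned in the SAP text lets a reader take them out again.

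Safety is a stated secondary objective, and the product is a single-dose imaging agent. The serious-event percentage is among the first safety figures a reader looks for, and it would be read in the sense of 10.1. The wording of 10.2 also leaves room for sites to differ, since one might report by grade and another only after judging seriousness. The SAP presents safety tables by centre, so any such difference would appear there.

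**Working it through.** The documents state no figure to reproduce, so the check is a comparison of texts, followed by the arithmetic that is possible.

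1. **Test case.** Take a laboratory value that was not Grade 3 at screening and is Grade 3 at Visit 4. It is asymptomatic, unrelated to prostate cancer and leads to no admission.
   - Under the grade sentence in Protocol 10.2 it is an SAE.
   - The two exemptions do not apply, because it is neither disease-related nor an unchanged pre-existing finding.
   - Under Protocol 10.1 it meets none of the five outcome criteria. It could enter only as an important medical event, which is conditional and not triggered by grade.
   - Under the sentence in 10.2 just before the grade rule it is an AE or SAE only if it meets the 10.1 definitions.
   - So one event gets different answers from sections 10.1 and 10.2, and from two neighbouring sentences within 10.2.

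2. **Grade 3 against Grade 4.** Table 1 in Protocol 10.4 describes Grade 3 as not immediately life-threatening, so grade alone cannot meet the life-threatening criterion. It also mentions admission being indicated, but 10.1 asks whether admission is required. Grade 4 is described by life-threatening consequences, which overlaps with 10.1. Even there, 10.1 asks whether the participant was at risk of death at the time of the event, and a grade does not establish that. The conflict is plain for Grade 3 and partial for Grade 4.

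3. **Can such a value reach the SAP count?** Protocol 7.5 names 5 haematology items (the white-cell count with its differential taken as one) and 14 biochemistry items: 5 + 14 = 19. Protocol 7.7 repeats the laboratory tests at Visit 4, recommended at about 2 weeks and allowed up to 6 weeks after the scan. Six weeks is 6 × 7 = 42 days, the limit of the TEAE summary window in SAP 6.1. The route is therefore open.

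4. **Can a reader separate the events afterwards?** The CTCAE-grade line in SAP 6.1 is not crossed with seriousness. The SAE listing has no stated field for the basis of seriousness. The AE fields named in Protocol 10.4 (description, dates, severity, relatedness, other suspect product, action taken) do not include a seriousness criterion.

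5. **Size.** Let k be the number of subjects whose only serious TEAE is one reported by the grade rule alone, and N the number in the safety set. The percentage of subjects with a serious TEAE then rises by 100 × k / N points. The documents give neither k nor N. As a range for N, assume at least the 85 evaluable patients of the interim analysis and at most the 180 planned. Each such subject then adds between 100 / 180 = 0.56 and 100 / 85 = 1.18 percentage points. With k = 0 the effect is nil.

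**The case against.** The strongest reply is that 10.2 should be read as a whole. The grade sentence carries its own qualifier, and the next paragraph supplies the exceptions it points to. A reader might infer that every Grade 3/4 laboratory value becomes an SAE; the text does not say that. One can go further and argue that the grade rule applies only to findings already judged clinically significant, since the sentence before it and Protocol 10.4 both use that filter. This is a fair reading, but it does not remove the conflict. Clinical significance is not seriousness, and a clinically significant Grade 3 value without any 10.1 outcome would still become an SAE by grade.

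Second, over-reporting laboratory grades to the sponsor may be deliberate caution. That is legitimate for reporting, but it does not settle what the published count should mean.

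Third, much of the material for a split may already exist. The SAP tabulates TEAEs by SOC, PT and grade, lists all SAEs, and lists laboratory values with abnormal findings flagged. The table and listing shells are in a separate document and the SAE form is not shown, so a seriousness-criterion field may exist. This stands, and it keeps the point minor.

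Fourth, Protocol 11.3 reports that recruitment has ended, and SAP Addendum 2 follows database lock. Clarifying the protocol now cannot change how sites classified events. This also stands, and it moves the useful part of the remedy to the SAP. Finally, no test or stopping rule in the documents depends on the serious-TEAE count.

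**Conclusion.** The inconsistency is real and minor. Protocol 10.2 assigns seriousness by laboratory grade, outside two exemptions, against 10.1, its closing note, 10.4 and the preceding sentence of 10.2 itself. Because SAP 6.1 does not define serious or split the count, any event that is an SAE only under the grade rule would be counted as serious.

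That consequence is conditional. It needs at least one non-exempt Grade 3/4 abnormality after injection that meets no 10.1 criterion, at a site that applied the rule as written. A reader might infer that the reported rate is in fact inflated, or that sites did differ; the documents contain no counts that show either. A reader might also put the rise at, say, 2 to 5 points by assuming that 2 to 5% of patients have a Grade 3/4 value after the scan. That would only restate the assumption, and it would ignore the exemptions. The supportable statement is that the size is unknown and may be zero.

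**What to change.** Reconcile Protocol 10.2 with 10.1 and 10.4, so that it is clear whether Grade 3/4 laboratory abnormalities are serious in the sense of 10.1 or are only reported through the SAE route. The 24-hour reporting to the sponsor in 10.5 need not change. The same edit can align the CTCAE version, which is v4.0 in 10.2 and 4.03 in 10.4.

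In SAP 6.1, by addendum, state the basis of seriousness. Then show serious TEAEs that meet a 10.1 criterion separately from those reported as SAEs only under the laboratory-grade rule. An extra row in the overall TEAE summary or a flag in the SAE listing would do. Addendum 2 already adds tables after database lock, so the route exists.

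The cost is a short review of each laboratory SAE to establish which 10.1 criterion, if any, it met, because the AE fields in 10.4 do not name one. The split should be labelled as defined after lock. If no event was an SAE by grade alone, the row reads zero and the question is closed.
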